10.4.1 Variable

The primary efficacy variable is the clinical benefit rate (CBR) (e.g. defined as CR, PR or SD) at week 24 by RECIST 1.1 for solid tumors and the Revised Response Criteria for Malignant Lymphoma, ([Cheson et al 2007](#)), for Lymphoma.

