- Unexplained loss of $> 10\%$ body weight within the previous 6 months, as assessed and reported (present vs. absent) by the Investigator.

4. Evaluation of Radiological Response

For the sake of simplicity, complete remission and complete response will both be referred to as complete response.

Definitions of Response for Lymphoma patients are listed in [Table 4-1](#). To evaluate disease response to treatment, all index and non-index lesions will be followed and assessed throughout the study. At each assessment, response is evaluated separately for the **index lesions** ([Table 4-1](#)) and **non-index lesions** ([Table 4-2](#)) identified at Screening, then a combined overall radiological response is determined ([Table 4-3](#)).

Table 4-1 Response Definition for Lymphoma

Response	Definition	Nodal Masses	Spleen. Liver	Bone Marrow
CR	Disappearance of all evidence of disease	a FDG-avid or PET positive prior to therapy; mass of any size permitted if PET negative b Variably FDG-avid or PET negative; regression to normal size on CT	Not palpable, nodules disappeared	Infiltrate cleared on repeat biopsy; if indeterminate by morphology, immunohistochemistry should be negative

Response	Definition	Nodal Masses	Spleen, Liver	Bone Marrow
PR	Regression of measurable disease and no new sites	
≥ 50% decrease in SPD of up to 6 largest dominant masses; no increase in size of other nodes
 
a FDG-avid or PET positive prior to therapy; one or more PET positive at previously involved site
 
b Variably FDG-avid or PET negative; regression on CT
	≥ 50% decrease in SPD of nodules (for single nodule in greatest transverse diameter); no increase in size of liver or spleen	Irrelevant if positive prior to therapy; cell type should be specified
SD	Failure to attain CR/PR or PD	
a FDG-avid or PET positive prior to therapy; PET positive at prior sites of disease and no new sites on CT or PET
 
b Variably FDG-avid or PET negative; no change in size of previous lesions on CT
		
Relapsed disease or PD	Any new lesion or increase by ≥ 50% of previously involved sites from nadir	
Appearance of a new lesion(s) > 1.5 cm in any axis, ≥ 50% increase in SPD of more than one node, or ≥ 50% increase in longest diameter of a previously identified node > 1 cm in short axis
 
Lesions PET positive if FDG-avid lymphoma or PET positive prior to therapy
	> 50% increase from nadir in the SPD of any previous lesions	New or recurrent involvement

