a. Evaluation of Index Lesions (nodal and extranodal)

i. When index nodal lesions are not in complete response

The response for index lesions is evaluated by calculating the Sum of the Products of Diameters (SPD) of all index lesions (see Table 4-2), except when there is a Complete Response for index nodal lesions (i.e. complete normalization of all index nodal lesions) (see [Section ii.](#)).

Table 4-2 Radiological status based on SPD calculation for all index lesions

Response Criteria ¹	Evaluation of index lesions
Complete Response (CR)	See Table 4-4 below (not based on SPD calculation for all index lesions)
Partial Response (PR)	At least 50% decrease from Screening in the SPD of all index lesions
Stable Disease (SD)	Failure to attain the criteria needed for CR or PR and failure to fulfill the criteria for PD
Progressive Disease (PD)	At least a 50% increase from nadir ² in the SPD of all index lesions

¹ At each assessment (if the index nodal lesions are not in CR status), the response status based on SPD calculation will be first assessed for meeting PD status criteria, then PR status and SD status.

² Nadir is defined as the smallest sum of the product of the diameters of all index lesions recorded so far, at or after Screening.

ii. When index nodal lesions are in complete response

When there is a Complete Response for index nodal lesions (i.e. complete normalization of all index nodal lesions as defined in [Section v.](#): all index lesion ≤ 15 mm in long axis), the SPD for these index nodal lesions may not be equal to zero and therefore a calculation of a SPD for all index lesions may be misleading. Therefore, by default, a specific response for extranodal index lesions needs to be evaluated, based on the SPD calculation restricted to all index extranodal lesions only (see [Table 4-3](#)).

Table 4-3 Radiological response criteria for index extranodal lesions in case of CR in index nodal lesions

Response Criteria ¹	Evaluation of index extranodal lesions
Complete Response (CR)	Complete disappearance of all index extranodal lesions
Partial Response (PR)	At least 50% decrease from Screening in the SPD restricted to all index extranodal lesions
Stable Disease (SD)	Failure to attain the criteria needed for CR or PR and failure to fulfill the criteria for PD
Progressive Disease (PD)	At least a 50% increase from nadir ² in the SPD restricted to all index extranodal lesions

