¹ At each assessment, response will be first assessed for meeting CR status. If CR status is not met, response will be assessed for PD status, then PR status and SD status.

² Nadir is defined as the smallest sum of the product of the diameters restricted to all index extranodal lesions recorded so far, at or after Screening.

The algorithm for evaluating the response integrating index extranodal lesions and the SPD calculated on all index lesions (where appropriate) provides an overall response for index lesions.

iii. Evaluation of response for all index lesions

The evaluation of response for all index lesions is based on the combination of the response for index nodal lesions (CR or non-CR), the response for index extranodal and the status based on the SPD calculated on all index lesions (nodal and extranodal), as described in Table 4-4.

Table 4-4 Radiological response for index lesions

Response for index nodal lesions ¹	Response for index extranodal lesions ¹	Status based on SPD calculation for all index lesions	Response for index lesions
CR	CR	Not calculated	CR
CR	SD/ PR	Not calculated	PR
CR	PD	PD	PD
CR	PD	PR	PR
CR	PD	SD	SD
Non-CR	Not evaluated	PD	PD
Non-CR	Not evaluated	PR	PR
Non-CR	Not evaluated	SD	SD

Response for index nodal lesions ¹	Response for index extranodal lesions ¹	Status based on SPD calculation for all index lesions	Response for index lesions
¹ If no index nodal lesions are present at Screening, then index lesions response is equal to the index extranodal lesions response. A similar rule applied if no index extranodal lesions are present at Screening, then index lesions response is equal to the index nodal lesions response.			

In case of missing measurements of any of the index lesions, the radiological response for index lesions at that assessment will be “Unknown (UNK)”, unless progression was seen.

All lesions must have been measured with the same method as the one used at Screening, otherwise the radiological response for index lesions at that assessment will be “Unknown (UNK)”.

iv. Evaluation of non-index lesions (including nodal, splenic and/or hepatic nodules and other extranodal lesions)

At each reassessment, a non-index lesion (or a group of non-index lesions) will be given one of the following designations:

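### Appendix 2 gives incompatible progression rules for DLBCL, so the same scan can be a clinical-benefit failure or a success

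*Protocol*

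**What the plan says.** All table numbers here are those of Protocol Appendix 2 unless stated otherwise (Protocol section 4 has a different Table 4-1).

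**Table 4-1.** The opening of Appendix 2 section 4 says that this table holds the lymphoma response definitions, and cites it again for index lesions. Its general PD definition is "Any new lesion or increase by ≥ 50% of previously involved sites from nadir". The nodal column includes "≥ 50% increase in longest diameter of a previously identified node > 1 cm in short axis", and adds the condition "Lesions PET positive if FDG-avid lymphoma or PET positive prior to therapy". The spleen and liver column is "> 50% increase from nadir in the SPD of any previous lesions", with no PET condition in that column.

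**Tables 4-2 to 4-6.** Table 4-2 calls PD for index lesions on "At least a 50% increase from nadir ² in the SPD of all index lesions". Once index nodes are normal, the text warns that a total over all index lesions can mislead, and Table 4-3 judges extranodal index lesions on their own. Table 4-4 then brings the total back through its column "Status based on SPD calculation for all index lesions". Nodal CR with extranodal PD becomes PR if the total is PR, and SD if the total is SD. Table 4-6 builds the overall radiological response from this result.

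**Cross-references.** The opening paragraph sends index lesions to Table 4-1, non-index lesions to Table 4-2 and overall response to Table 4-3. The tables that actually do these jobs are 4-2 to 4-4, 4-5 and 4-6.

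**Endpoint.** Protocol section 10.4.1 defines CBR as CR, PR or SD at week 24. SAP section 2.5.2 uses best overall response within the first 24 weeks. The SAP adds no lymphoma-specific growth rule.

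**The concern.** DLBCL is one of the seven cohorts judged on CBR, and SD or PR counts as success while PD does not. If a growing lesion is PD in one table and is offset by shrinkage elsewhere in another, the table that a reader follows decides the patient's outcome. Assessment is local, so sites may follow different tables. SAP section 2.5.2 also counts progression recorded as the reason for stopping treatment, so a site's reading can enter CBR by that route as well. PFS, TTP and DOR depend on the same call. Protocol section 10.4.5 and SAP section 2.5.4 plan no supportive or sensitivity analysis that would show the difference.

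**Working it through.** The lesion sizes below (in mm) are assumptions chosen to test the rules. SPD is the sum of the products of the two diameters. The PR rule is "At least 50% decrease from Screening in the SPD of all index lesions".

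**Plan figure.** The only plan figure used is the 25% historical DLBCL rate (Protocol Table 10-1). With median PFS of 3 months, exponential PFS and 24 weeks taken as 6 months, 0.5^(6/3) = 0.25, which agrees.

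**1. First post-baseline scan, week 12, with a liver lesion.** Liver lesions are extranodal under Appendix 2 section 1, and Protocol section 7.2.1.1.4 lets them be index lesions.
- Screening: three nodes 60x50 and one liver nodule 20x20. SPD = 3(3000) + 400 = 9400.
- Week 12: nodes 15x14 (normal, since the long axis is at most 15) and liver 30x25. SPD = 3(210) + 750 = 1380.
- Liver: 750/400 = 1.875, or +87.5%. This is PD in Table 4-1 and extranodal PD in Table 4-3.
- Total: 1380/9400 = 0.147, or -85.3%. The status is PR, so Table 4-4 gives PR.
- No earlier SD exists and no PET condition applies. The choice of table decides failure or success under either CBR wording.

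**2. A single node.** Nodes 20x15, 60x50 and 40x40; the first grows to 30x20.
- SPD goes from 300 + 3000 + 1600 = 4900 to 600 + 3000 + 1600 = 5200, or +6.1%. Table 4-2 gives SD.
- Longest diameter is 30/20, or +50%, with short axis above 10. Table 4-1 gives PD, provided its PET condition is met or does not apply.
- In general, let the growing node hold a share f of the nadir SPD, with the rest stable. If both axes grow 50%, the total rises by f(1.5² - 1) = 1.25f, which reaches 50% only when f is at least 0.40. If only the long axis grows, the total rises by 0.5f, so f must be 1.

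**3. The opposite direction.** One index node grows from 40x30 to 49x37.
- SPD: 1813/1200 = 1.511, or +51.1%. Table 4-2 gives PD.
- Longest diameter: 49/40, or +22.5%, and only one node is involved. Neither growth criterion in Table 4-1's nodal column is met. Only its general phrase about involved sites, which names no measure, might apply.

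**4. Response first, liver growth later.** Node 50x40 and liver 20x20 at baseline (2400); 25x20 and 15x15 at nadir (725); then 14x10 and 25x25 (765).
- Last scan: liver 625/225 is +178%, so PD in Table 4-1. The total is +5.5% from nadir and -68.1% from baseline, so Table 4-4 gives PR.
- Nadir scan: 725/2400 is -69.8%, so PR in Table 4-2 and at least SD in Table 4-1. If that scan falls by week 24, the SAP wording counts a success under both rules. Under the protocol's week-24 wording, the result still turns on the table if the last scan is the week-24 scan.

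**5. Size.** One patient is 1/10 = 10 points, or 1/24 = 4.2 points. As a stand-alone illustration, take an exact binomial test at 0.20 against 25%, the comparison analysis in Appendix 4 section 8. P(X ≥ 9 of 24) = 0.121 passes and P(X ≥ 8 of 24) = 0.234 does not. This is not the planned hierarchical analysis.

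**The case against.** The strongest reply is that Tables 4-2 to 4-6 form an explicit calculation chain, that the mismatched cross-references look like a numbering slip, and that the two disputed Table 4-4 rows are written out and so look deliberate. These tables may well be the intended operating rules. But the text never says so. Table 4-1 is still introduced as the definitions, and correcting the numbers would leave its PD criteria in conflict with the chain.

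A second reply is that the new-lesions rule already calls PD on 50% long-axis growth of an abnormal lymph node. Appendix 2 section 2b defines such a node as not being a lesion, so the clause does not reach index nodes, and it cannot reach extranodal lesions.

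Three limits stand:
- Table 4-1's nodal PD carries a PET condition, while PET is scheduled only at screening and to confirm CR (Protocol Table 7-1 and section 7.2.1.1.7). Step 2 is therefore conditional; step 1 is not.
- The SAP's best-response wording protects patients who already had SD or PR by week 24, as step 4 shows.
- A reader might infer that the working tables push CBR upward. The documents do not support that. Step 3 goes the other way, Table 4-2 needs no PET, and the new-lesions rule sets no size floor for a discrete extranodal lesion, whereas Table 4-1's nodal column requires more than 1.5 cm.

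**Conclusion.** The conflict is real and reaches the primary endpoint. Under the SAP wording it can change a DLBCL patient's CBR status when the scan is the first post-baseline one. Under the protocol wording it can do so at later scans as well. Each affected patient is worth 10 points at n=10 or about 4 points at n=24. How many patients are affected, and the net direction, cannot be obtained from the documents.

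Two stronger readings are not supported. One is that Table 4-1 must be the governing rule: no text establishes precedence either way, and progression also bears on stopping treatment, so the passages need reconciling by the sponsor. The other is that the remaining six cohorts are materially affected. They are touched only through borrowing, and that effect has not been calculated.

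The conclusion rests on the tables as written and on assumed lesion sizes that meet their measurability rules.

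**What to change.** The sponsor should:
- reconcile Table 4-1 with Tables 4-2 to 4-6, in particular the Table 4-4 rows CR/PD/PR and CR/PD/SD;
- state one governing progression rule for the DLBCL endpoints, including how the PET condition applies when no PET is scheduled at suspected progression;
- correct the cross-references in the opening paragraph of Appendix 2 section 4;
- derive every DLBCL response used for CBR, PFS, TTP and DOR under that one rule, from the lesion measurements already in the eCRF;
- report the other rule as a sensitivity analysis.

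The cost is appendix wording and some programming. If the PET condition is kept, lesion sizes alone cannot verify it, so the handling of scans without PET must be written down. DLBCL results may shift in either direction.

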vi. Overall radiological response

Overall radiological response is calculated as shown in Table 4-6.

Table 4-6 Overall radiological response at each assessment

Index lesions	Non-index lesions ¹	New lesions	Overall radiological response
CR	CR	No	CR
CR	SD	No	PR
PR	CR or SD	No	PR
SD	CR or SD	No	SD
PD	Any	Yes or No	PD
Any	PD	Yes or No	PD
Any	Any	Yes	PD

¹If no non-index lesions are present at Screening, then this column is not used in evaluating overall radiological response.

If the evaluation of any of the index or non-index lesions identified at Screening could not be made during follow-up or if the index or non-index response is “Unknown (UNK)”, the overall response status at that assessment must be “Unknown (UNK)” unless progression or a new lesion was seen.

vii. Evaluation of overall disease response

The evaluation of overall disease response at each assessment is a composite of the individual radiological responses (index and non-index lesions, new lesions), laboratory test (bone marrow) and clinical responses (lymphoma related clinical symptoms).

viii. Bone marrow re-assessment at time of radiological CR

In order to confirm a Complete disease response (CR), bone marrow biopsy or aspirate may be required when a radiological CR has been achieved. Details are provided in the Study Protocol. The infiltrate of lymphoma in bone marrow must have cleared on repeat bone marrow biopsy or aspirate. Patients who achieve a CR by other criteria but who have persistent morphologic positive or inconclusive bone marrow involvement will be considered partial responders. New or recurrent bone marrow involvement anytime during the follow up will be considered PD. Bone marrow biopsy or aspirate will be performed after the first assessment of CR or when clinically indicated.

The biopsy sample of bone marrow must be adequate (with a goal of > 20 mm unilateral core). If the sample is indeterminate by morphology, it should be negative by immunohistochemistry.

ix. Overall disease response

If a patient has an overall radiological response of CR then this response must be confirmed by bone marrow biopsy or aspirate (if required as per the Study Protocol), presence of normal liver and spleen size, and evaluation of lymphoma related B-symptoms. The patient's overall response will be calculated as follows:

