A patient will be deemed to have overall disease response of CR if bone marrow biopsy or aspirate becomes negative for tumor involvement (if the bone marrow was involved by lymphoma at Screening) and the liver and spleen are normal in size and there are no lymphoma related B-symptoms in addition to radiological CR.

If assessments of any of the following: lymphomatous infiltration of bone marrow (If required as per the Study Protocol), or evaluation of B-symptoms is not done, unknown or indeterminate or B-symptoms are still present when the overall radiological response is assessed as CR or the liver or spleen are enlarged, then the overall disease response will be assessed as PR until evaluation of these factors have shown normalized results and recorded on the corresponding eCRF.

For patients whose radiological response is anything other than CR, assessment of bone marrow, liver, spleen and B-symptoms will not be required in evaluating overall response and overall disease response is the same as radiological response. However any new or recurrent bone marrow involvement at any time during follow-up will be considered PD.

Of note, appearance of B-symptoms or enlarged spleen or liver will not in themselves constitute documentation of progression. They are however expected to be associated with progressive disease. Every effort should be made to document that evidence radiologically and report the corresponding tumor assessments. Such tumor assessments are expected to be performed within 2 months of appearance of B-symptoms or enlarged spleen or liver.

5. References (available upon request)

Cheson BD (2007a) The international harmonization project for response criteria in lymphoma clinical trials. Hematol Oncol Clin N Am 21:841-854.

Cheson BD (2009) The case against heavy PETing. *J Clin Oncol* 27:1742-1743.

Cheson BD, Pfistner B, Juweid ME, et al (2007b) Revised response criteria for malignant lymphoma. *J Clin Oncol* 25:579-586.

FDA Guideline (2005) Clinical Trial Endpoints for the Approval of Cancer Drugs and Biologics, April 2005.

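### Minor: Appendix 2 calculates DLBCL response without the PET required to confirm CR, so a CT-normal, PET-positive patient is CR by section ix but PR or SD by Table 4-1

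*Protocol*

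**What the plan says.** **Calculation rule (Appendix 2, sections vii and ix).** Section vii describes overall disease response as "a composite of the individual radiological responses (index and non-index lesions, new lesions), laboratory test (bone marrow) and clinical responses", the last meaning lymphoma symptoms. Section ix says that a radiological CR "must be confirmed by bone marrow biopsy or aspirate (if required as per the Study Protocol), presence of normal liver and spleen size", along with B-symptoms. It introduces its rule by saying that the patient's "overall response will be calculated as follows". It then states: "A patient will be deemed to have overall disease response of CR if bone marrow biopsy or aspirate becomes negative for tumor involvement" (where marrow was involved at screening), provided that liver and spleen are normal, B-symptoms are absent and there is a radiological CR. If marrow or B-symptoms are unassessed or unclear, if B-symptoms persist, or if liver or spleen is enlarged, "then the overall disease response will be assessed as PR until evaluation of these factors have shown normalized results". PET appears in none of these.

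**Radiological CR (Appendix 2, section 2c and Tables 4-2 to 4-6).** This rests on CT/MRI lesion status. An index node counts as normal at a long axis of 15 mm or less; an extranodal lesion must vanish.

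**Response definitions (Appendix 2, Table 4-1).** For disease that was PET positive before therapy, the CR row reads "mass of any size permitted if PET negative". The PR row asks for at least a "50% decrease in SPD of up to 6 largest dominant masses" and, in the same disease, "one or more PET positive at previously involved site". The SD row covers earlier sites that remain PET positive with no new sites.

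**Scan requirement.** Section 7.2.1.1.7 and Table 7-1 call for a PET at screening and another to confirm CR. Neither assigns a category if the second scan is positive, missing or indeterminate.

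**SAP.** Section 2.7.1 sends response in hematological tumors back to the protocol appendix and adds no PET rule.

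**The concern.** The appendix holds two rules for the same patient, and they disagree when CT has normalized but an earlier site is still PET positive. Section ix is the one written as a calculation, and followed literally it returns CR. Table 4-1 does not.

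The contrast with bone marrow is telling. Section ix imports the marrow requirement from the protocol body and says what happens when the result is unavailable. The PET requirement gets neither, although section 3.a.i of the appendix explains how to read a PET as positive.

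At stake is the DLBCL response table. SAP section 2.7.2 reports response categories separately for each hematological tumor type, so the CR and PR rows depend on which rule is used. Where Table 4-1 gives SD, the patient also stops being a responder. ORR then loses one, time to response (TTR) loses an event, and duration of response (DOR), which SAP 2.7.2 analyses with all tumor types combined, loses one responder.

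**Working it through.** The plan states no figure here to reproduce. The check sets the two rules side by side and then sizes the difference. The lesion sizes are illustrative.

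**Inputs**
- Entry node size: at least 2 cm (protocol 5.3), above 20 mm (Appendix 2, section 2a). A 21 mm node meets both.
- Normalized node: long axis 15 mm or less (Appendix 2, section 2c).
- PR threshold: SPD down at least 50% (Table 4-1).
- Endpoints: CBR counts CR, PR and SD (protocol 10.4.1); ORR counts CR and PR (protocol 10.5.1).
- Cohort sizes: 10 before expansion, 24 in the primary population, 30 with up to 6 pre-exposed patients (protocol 4.3; Appendix 4, section 3).

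**The two rules compared.** Take one index node, no non-index or new lesions, clear marrow, normal liver and spleen, no B-symptoms, and an earlier site still PET positive.

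| Node, mm | SPD, mm² | Change | Section ix | Table 4-1 |
|---|---|---|---|---|
| 40×30 to 15×12 | 1200 to 180 | 180/1200 − 1 = −85.0% | CR | PR |
| 25×20 to 15×12 | 500 to 180 | 180/500 − 1 = −64.0% | CR | PR |
| 21×12 to 15×12 | 252 to 180 | 180/252 − 1 = −28.6% | CR | SD |

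**When Table 4-1 can give SD.** Let L be the baseline long axis of a single node that shrinks to 15 mm.
- Both axes shrink in proportion: SPD falls less than 50% if (15/L)² > 0.5, so L < 15/√0.5 = 21.2 mm.
- Short axis unchanged: 15/L > 0.5, so L < 30 mm.
- With several index nodes, at least one must fall by less than 50%, because if each fell by 50% or more the sum would too.
- Index extranodal lesions must disappear, so they cannot produce the SD case alone.

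**Shift per affected patient**

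| Cohort n | CR row, 100/n | ORR if Table 4-1 gives PR | ORR if Table 4-1 gives SD | CBR |
|---|---|---|---|---|
| 10 | 10.0 points | 0 | 10.0 points | 0 |
| 24 | 4.2 points | 0 | 4.2 points | 0 |
| 30 | 3.3 points | 0 | 3.3 points | 0 |

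CBR does not move because CR, PR and SD all count. The posterior probabilities behind futility, expansion and final success use CBR data only, so they do not move either.

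**The case against.** The best defense is that the documents, read together, already give the right answer. A scan ordered to confirm CR does not confirm it when positive. Table 4-1 is introduced as the set of lymphoma response definitions, and section ix never says that PET is to be ignored. Response is the local investigator's assessment, and where Appendix 2 mentions a sponsor-calculated response, the investigator's justified assessment may replace a calculated unknown. Most of this stands: an investigator who applies Table 4-1 classifies the patient correctly. It does not remove the conflict, because section ix is the stated calculation and no text says which rule governs.

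It is also fair that the consequences are small. The tables are descriptive, and with fewer than 4 patients in a hematological tumor type SAP 2.7.2 gives only a listing. DLBCL has the slowest assumed accrual, 6 per year. The SD case needs nodes close to the entry size unless the short axis barely shrinks.

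Four stronger readings are tempting, and the documents do not support them:
- *The primary analysis is biased.* CBR does not distinguish CR, PR and SD.
- *DLBCL complete responses will be overcounted.* No document says that section ix will be programmed against the investigator's assessment, or how many patients would be CT-normal and PET-positive.
- *The SD-case patient leaves the TTR analysis.* SAP 2.7.1 includes all patients in TTR; the patient changes from event to non-event.
- *DLBCL duration of response is distorted.* SAP 2.7.2 pools all tumor types for DOR, which dilutes one DLBCL patient.

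**Conclusion.** The point holds as a minor error in the text as written: applied literally, section ix gives CR to a patient whom Table 4-1 classes as PR or SD. In the PR case the effect stops at the DLBCL CR/PR split, at 10, 4.2 or 3.3 points per affected patient. In the small-node SD case it also reaches ORR by the same amount, TTR, and the pooled DOR responders.

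This assumes that the assessment in question determines the patient's best overall response, that no other node has grown, and that section ix is followed literally. The conflict between the rules is certain from the text; the number of affected patients is unknown and could be zero.

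**What to change.** In Appendix 2, section ix:
1. Add to the CR conditions: *PET negative, if FDG-avid or PET positive at screening*.
2. State that if the confirming PET is positive at an earlier site, not done or indeterminate, the patient is not CR. The category is PR if SPD fell at least 50% and otherwise SD, until a negative PET is recorded.

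In section vii, add PET to the components of overall disease response.

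Item 2 deliberately treats a missing PET like a positive one. Adding a missing PET to the existing list that defaults to PR would make a small-node patient SD when scanned and PR when not, so skipping the scan would earn a better category.

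The cost is a few words and no new scan, since both PETs are already required. The SAP history already records changes after database lock. If amending the protocol is no longer practical, one sentence in the SAP or study report naming the rule used would remove the ambiguity.

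The reverse mismatch remains: a PET-negative residual node above 15 mm is CR by Table 4-1 but not by Tables 4-2 to 4-6. It could be settled in the same edit.
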